3.7.1.2.2 Response to Treatment

This secondary analysis of the primary efficacy is the proportion of subjects in each treatment group who respond to the treatment. “response” is defined as > 50% decrease of HRSD score at the end of the acute treatment phase. The null hypothesis is that there is no difference between the treatment and sham groups in the proportion of subjects who respond to the treatment at the end of the acute treatment phase. The primary variable is defined in Section 2.4.1. The logistic model will include three covariates, PTSD diagnosis, History of substance abuse, and Site. The number and percentage of subjects in remission at the end of the acute treatment will be summarized (Table 3.7.3a-c). Odds ratio and 95% confidence interval (CI) will be presented using SAS PROC GENMOD. If the coefficient for treatment effect is significant (i.e., the confidence interval for the odds ratio does not include 1), then the null hypothesis will be rejected (Table 3.7.4a-c).

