3.1.2 Analysis Conventions

This section details general policies to be used for the statistical analyses. Departures from these general policies may be given in the specific detailed sections of this statistical analysis plan. When this situation occurs, the rules set forth in the specific section take precedence over the general policies. The following policies will be applied to all data presentations and analyses.

- All statistical tests will use a significance level of $\alpha = 0.05$. Two-tailed tests will be performed for all analyses that use statistical testing.
- All p-values will be rounded to 3 decimal places. All p-values that round to 0.000 will be presented as '<0.001' and p-values that round to 1.000 will be presented as '>0.999'. Any p-value $\leq \alpha$ will be considered statistically significant.
- Summary statistics will consist of the number and percentage of responses in each category for discrete variables, and the mean, median, standard deviation (SD), minimum, and maximum for continuous variables.
- All mean and median values will be formatted to one more decimal place than the measured value. Standard deviation values will be formatted to two more decimal places than the measured value.
- All percentages will be rounded to one decimal place. The number and percentage of responses will be presented in the form XX (XX.X), where the

- percentage is in the parentheses. The decimal of the percentage may be dropped due to space constraints when creating a table.
- For a continuous variable, if it is normally distributed or approximately normally distributed, Student t test and/or the general linear regression will be performed to test the group difference as proposed in the analysis plan, otherwise, Wilcoxon test and/or a quantile regression will be used as an alternative analysis method; for a categorical variable, Pearson χ^2 test and/or a corresponding generalized linear regression will be performed to test the group difference.
 - All listings will be sorted for presentation in order of treatment group, site number, subject number, and date of procedure or event.
 - All analysis and summary tables will have the population sample size for each treatment group in the column heading.
 - Calculating change from baseline to a visit will be done as follows: change = visit –baseline.

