3.7 Efficacy Analyses

The primary endpoint analysis will be done for the ITT population. All secondary and other efficacy analyses will be done for the ITT, completer, and fully compliant populations, unless otherwise specified. Potential difficulties of convergence of model fit, which arise in efficacy analyses that include covariates, will be handled using the method described in Section 3.7.1.

At the completion of the follow-up phase for all subjects in the clinical trial, the efficacy endpoints analyses will be performed. The primary efficacy analysis is based on the measurements of Hamilton Rating Scale for Depression (HRSD). The other key efficacy analyses will include:

- Depression measured by Montgomery-Asberg Depression Rating Scales (MADRS)
- Depression measured by Beck Depression Inventory (BDI)
- Suicide Ideation measured by Beck Scale for Suicide Ideation (BSS)
- Quality of Life measured by the VR-36
- Cognitive Function as measured by a neuropsychological battery

All endpoints will be summarized for all visits once the study is complete.

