3.7.1.2.1 Durability of Remission

The durability of remission is the subjects in each treatment group who sustain “remission” from depression after 24 weeks post-treatment at the end of the follow-up phase. “Remission” is assessed by a HRSD score ≤ 10 at the end of the follow-up phase. The null hypothesis is that there is no difference between the treatment and sham groups in the time to recurrence of subjects who sustain remitted after 24 weeks

post-treatment at the end of the follow-up phase. If a subject is no longer remitted at a certain follow-up time point t based on the criteria, then the subject fails and the failure time is the study day of failure (X_{ij}). Durability is calculated by subtracting the date which the subject first becomes remitted from the date of recurrence. Similarly, if a subject remains remitted at a certain follow-up time point, then the subject is censored and the censoring time (C_{ij}) is the date of censoring minus the study day on which the subject became remitted. Group differences will be tested based on the Log-rank test (Mantel 1966). Both Kaplan-Meier estimates (Kaplan and Meier 1958) and the Log-rank statistics will be obtained using PROC LIFETEST (Tables 3.7.2a-c). The survival distribution of durability of remission between the two treatment groups will be plotted using Kaplan-Meier curves (Figures 3.7.2a-c).

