3.7.2.6 Secondary Endpoint Analysis Results

The secondary endpoints are defined as severity improvements of MADRS, BSS, BDI, VR-36, and Cognitive function from baseline to end of the acute treatment. Given the several simultaneous hypothesis testing, multiplicity adjustment will be applied. The significance level for the secondary endpoint analyses will be 0.01. The analysis results can be extracted from the above analysis at the time point of end of acute treatment as shown in Table 3.7.34a-c.

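### Outside the primary test and the five secondaries held to 0.01 at end of acute treatment, every efficacy test defaults to 0.05 with no stated status, so HRSD response and QIDS-C16 face an easier threshold than MADRS

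*SAP*

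**What the plan says.** **General rule (3.1.2).** "All statistical tests will use a significance level of" 0.05, two-sided, and any p-value at or below that level counts as statistically significant. Where a later section departs from this, "the rules set forth in the specific section take precedence over the general policies".

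**The one efficacy override (3.7.2.6).** "The significance level for the secondary endpoint analyses will be 0.01". It is justified by the number of simultaneous hypotheses. It covers MADRS, BSS, BDI, VR-36 and cognition, from baseline to end of acute treatment.

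**Tests with no level of their own:**
- 3.7.1.2, HRSD: durability, response, short-term remission, long-term remission and score over time. The first four state a null; for durability, "The null hypothesis is that there is no difference between the treatment and sham groups in the time to recurrence". Score over time states none. Response is introduced in 3.7.1.2.2 with "This secondary analysis of the primary efficacy is the proportion of subjects in each treatment group who respond to the treatment". Only response has a rejection rule, based on the 95% confidence interval for the odds ratio.
- 3.7.3: QIDS-C16 and BHS, each as a score over time and as a severity class.
- 3.7.2: the over-time models of the named secondaries, and the severity models for MADRS and BDI.

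**Populations (3.7).** "All secondary and other efficacy analyses will be done for the ITT, completer, and fully compliant populations".

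**The concern.** The plan accepts that several simultaneous tests need a stricter level, applies it to one block of outcomes at one time point, and leaves the rest at 0.05. Two things follow.

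First, the thresholds run against the plan's own ranking. Outcomes under Other Efficacy Analyses, and an HRSD response analysis missing from both secondary lists, are judged at a level five times looser than the named secondaries.

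Second, if the primary remission test misses, the written rules still let a report reject the null for HRSD response, or call long-term remission, durability or QIDS-C16 statistically significant, without a caveat. The SAP says (1.0) that it will guide the final report and possibly publications, so the status of these p-values should be settled in it.

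**Working it through.** **1. The plan's own figure.** A Bonferroni split over five outcomes gives 0.05 / 5 = 0.01, as stated. Five independent tests at 0.01 give 1 − 0.99^5 = 0.049. This counts VR-36 and cognition as one test each.

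**2. Which level applies at end of acute treatment.**

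| Outcome | Tier by heading | Level | p = 0.03 is |
|---|---|---|---|
| HRSD remission (3.7.1.1) | Primary | 0.05 | significant |
| MADRS (3.7.2.6) | Secondary | 0.01 | not significant |
| HRSD response (3.7.1.2.2) | Additional analysis of the primary measure | 0.05, by 95% CI | significant |
| QIDS-C16 (3.7.3.1.1) | Other | 0.05, by default | significant |

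**3. What the looser level is worth.** An outcome with 80% power at two-sided 0.01 has a standardised shift of 2.576 + 0.842 = 3.417. At two-sided 0.05 its power is Φ(3.417 − 1.960) = Φ(1.457) = 0.93.

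**4. Chance of at least one false positive (illustration).** Inputs: 0.05 two-sided from 3.1.2; one ITT test per analysis; all nulls true. The SAP gives no correlation, so a common value ρ between test statistics is assumed and varied.

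- k = 5: the five HRSD analyses in 3.7.1.2.
- k = 9: those five plus QIDS-C16 score and severity and BHS score and severity.
- For ρ = 0: 1 − 0.95^k, so 1 − 0.95^5 = 0.226 and 1 − 0.95^9 = 0.370.
- For ρ > 0: Z_i = √ρ·F + √(1−ρ)·E_i with F and E_i independent standard normal, and the probability that max|Z_i| exceeds 1.960.

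| ρ | k = 5 | k = 9 |
|---|---|---|
| 0 | 0.226 | 0.370 |
| 0.5 | 0.183 | 0.269 |
| 0.8 | 0.127 | 0.166 |

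**5. At least one of the five significant while the primary is not.** With the primary as a sixth test of the same correlation: 0.95 × 0.226 = 0.215 at ρ = 0, 0.157 at 0.5 and 0.089 at 0.8.

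**6. What is left out.** The per-visit tests, the over-time and severity tests in 3.7.2, and the Completer and Fully Compliant repeats are not counted. They would add to the total, but by how much depends on correlations and population sizes that the SAP does not give.

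**The case against.** There is one primary hypothesis, one endpoint and one test. The headings then rank the rest as additional analyses of the primary measure, secondary, other and additional, and QIDS-C16 and BHS are not among the key efficacy analyses listed in 3.7. In a phase II trial, how strictly to control error below the secondary tier is partly a matter of judgement. This stands as far as it goes. A reader might infer that there is no hierarchy at all, and the headings show otherwise. But a heading does not switch off the rule in 3.1.2, and neither 3.7.1.2 nor 3.7.3 calls its tests exploratory or nominal.

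A reader might also infer that all five HRSD analyses are formally decided hypotheses. They are not: four state a null, and only response has a rejection rule.

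A single percentage for the false-positive risk would claim too much. A common correlation fits these tests poorly: short-term remission is close to the primary endpoint itself, the severity classes are cut from scores already counted, and durability concerns remitters. This objection stands, so only a range is given.

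The MADRS comparison holds only for the 3.7.2.6 endpoint. The MADRS over-time and severity tests in 3.7.2.1 carry no 0.01 level and also default to 0.05. That limits the contrast but widens the gap to be closed.

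Finally, response could be read as covered by the 0.01 level because it is called secondary. Section 3.7.2.6 names its endpoints and response is not one of them, and a 95% interval rule is a 0.05 test.

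**Conclusion.** The concern holds as a defect in stated rules: 3.1.2, 3.7.1.2.2 and 3.7.2.6 together let response, QIDS-C16 and BHS be declared significant at 0.05 when the named secondaries need 0.01 at the same time point. That part rests on the text alone.

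The size is illustrative: about 13% to 23% for the five HRSD analyses and 17% to 37% for nine tests, for an assumed common correlation from 0.8 down to 0, one ITT test per analysis and all nulls true.

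A reader might infer that the trial's main conclusion is at risk. The SAP does not support that: the primary test stays a single two-sided 0.05 test, and the inflation concerns supportive claims only. The change should be made, but it does not affect the validity of the primary analysis.

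**What to change.** - In 3.1.2 and 3.7, state that efficacy claims rest only on the 3.7.1.1 logistic regression test at 0.05 and the 3.7.2.6 endpoints at 0.01, all in ITT.
- State that every other efficacy test is supportive, reported with estimates, 95% confidence intervals and nominal p-values. Name 3.7.1.2, 3.7.3, the over-time and severity analyses in 3.7.2, and the Completer and Fully Compliant repeats, so that none is left without a status.
- In 3.7.1.2.2, replace the rejection rule with nominal reporting. If a claim on response is wanted, test it in ITT at 0.05 only after a significant primary result.
- Keep the 0.05 convention for model-building, baseline and safety tests. The over-time models use statistical significance to decide whether to drop the treatment-by-visit interaction, so confining the convention to efficacy claims would leave that step without a threshold.

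The cost is SAP wording only, with no new data or analyses. Section 1.0 says the plan precedes any analysis of the data, so the change can be made without knowledge of results. The downside is that response, durability, long-term remission, QIDS-C16, BHS and the other supportive tests can no longer be called significant on their own; response could be, if gated, only after a positive primary result.

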3.7.1.2.3. Remission Rates from Baseline to the Acute Treatment (Short term efficacy)

These endpoints are the proportions of subjects in each treatment group who are remitted at end of acute treatment. The null hypothesis is that there is no difference between the rTMS and sham groups in the proportions of subjects who are remitted across those time points after the acute treatment. The criteria to define the

remission are described in Section 3.7.1. The number and percentage of subjects' remission at the baseline and end of each five sessions the acute treatment will be summarized (Table 3.7.5). Odds ratio and 95% confidence interval (CI) will be presented using SAS PROC GENMOD. SAS PROC GENMOD will be used to run logistic regressions and odds ratios and their 95% confidence intervals will be presented. Further, the generalized linear mixed model will be applied to test the differences of the proportions of subjects' remission across all the time point (Breslow and Clayton 1993). The link function will be logit. SAS PROC GLIMMIX will be used to analyze the data (Tables 3.7.5a-c). The generalized linear mixed model will include three covariates, PTSD diagnosis, History of substance abuse, and Site.

3.7.1.2.4. Remission Rates from End of the Acute Treatment to End of the Follow-up (Long term efficacy)

These endpoints are the proportions of subjects in each treatment group and the data collected from the end of acute treatment to the end of follow-up. The analytic technique is parallel to those described above in Section 3.7.1.2.3. The null hypothesis is that there is no difference between the rTMS and sham groups in the proportions of subjects who are remitted across those time points from the end of the acute treatment to the end of follow-up. The results will be shown in Tables 3.7.6a-c).

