2.6 Sample Size Consideration

The primary hypothesis of the study is that in VA patients with TRMD, rTMS will result in a greater remission rate at the end of acute treatment than sham rTMS. The primary outcome measure in this study is success or failure to achieve remission from depression as defined by a score on the Hamilton Rating Scale for Depression (HRSD24) of 10 or less. The primary analysis will be done as an "intent-to-treat" analysis, i.e. patients will be analyzed in the groups to which they were randomized and drop-outs will be considered treatment failures. The primary hypothesis will be addressed using a logistic regression model with PTSD diagnosis, history of substance abuse, and site as covariates. Based on review of the studies reported in the Introduction Section, the Planning Committee felt that a 10% difference between treatments would be of clinical relevance given the severity of the illness. With a sample size of 180 per group, the proposed study will have a power of 81% to detect an absolute difference between groups of 10% in the percentage of those participants who remit (6% sham and 16% rTMS). Thus, a total of 360 patients are required. This goal of 360 patients, larger than any previous study, also provides a measure of protection should some assumptions be wrong.

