3.0 STATISTICAL METHODS

3.1 Statistical Handling Policy

3.1.1 Missing Data and Imputations

For subjects who drop out during the treatment phase will be considered as treatment failures for the purpose of the primary analysis and the missing values will not be imputed. Multiple imputation (MI) method may be used for certain secondary analyses. Multiple imputations will be based on Rubin's procedure (Rubin 1987) using SAS PROC MI and PROC MIANALYZE if needed. Sensitivity analysis will be performed to compare the results from the imputed data based on the two methods, and the complete data without imputation.

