3.7.1.2.5. HRSD Score Over Time

HRSD score at the baseline, end of each treatment block, and end of every four week follow-up time will be tested between the two treatment groups using SAS PROC GLM at each visit. A mixed regression model will be used to test the main effects of treatment using SAS PROC MIXED across all time visits. The model will include week, treatment and treatment by week interaction adjusted for the baseline. A means model will be assumed. An unstructured covariance model will be used in the analysis. If the model fails to converge a compound symmetry covariance matrix will be assumed. The restricted maximum likelihood (REML) method will be used to estimate the covariance parameters. If the treatment by week interaction is not statistically significant then this term will be removed from the final model. The repeated factor will be visit; all other variables will be considered as fixed effects. The model is defined as follows:

$$Y_{ijk} = \mu + \tau_k + B_j + \varepsilon_{ijk}$$

where Y_{ijk} is the HRSD scores measured on k^{th} treatment and on j^{th} visit for i^{th} subject, μ is the overall mean, τ_k is the mean effect of the treatment and the interaction, B_j is the random effect, and ε_{ijk} is the error (Laird et al 1982). The sample sizes, least-squares means, and standard deviations will be presented at each visit by treatment arm for each study visit (Tables 3.7.7a-c). The assumptions relating to the mixed-effects model will be reviewed by examining residual graphs. Scatter plots of residuals will be used to examine deviations from normality and to assess lack-of-fit. The least square means (LS-means) and their standard errors at each visit will be plotted by treatment groups (Figures 3.7.3a-c).

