37	Adverse Events (AE) and ADE and Serious Adverse Events (SAEs) and UADE	As required														

*B= Baseline

*S= Screening

¹ Sessions 21-25 (block 5) and 26-30 (block 6) may not be required if patient goes into remission earlier

² Must be conducted within 7 days prior to randomization

³ Termination Form will be completed at the end of the study OR when a patient decides to end study participation prior to the study completion date; i.e., a patient decides to withdraw or leave the study for any reason, withdraws consent, or is suspended from the study.

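### Block-by-block remission and score tests have no rule for patients who stop acute sessions on remission, so by default early remitters drop out of the session-25 comparison, and possibly session 30

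*SAP*

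**What the plan says.** **Early exit.** Footnote 1 of the SAP's Appendix 5.2 reads: "Sessions 21-25 (block 5) and 26-30 (block 6) may not be required if patient goes into remission earlier". The schedule brackets the session-25 column and labels the next one 30/last. As printed, the rows for HRSD/MADRS, BDI and QIDS-C16 carry six acute marks and none in taper weeks 1-3, and resume in follow-up. BSS and BHS are also marked in the taper weeks.

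**Block analyses.** Section 3.7.1.2.3 plans counts and percentages ("remission at the baseline and end of each five sessions the acute treatment will be summarized"), logistic odds ratios from GENMOD, and a GLIMMIX model over all time points. Section 3.7.1.2.5 says that the HRSD score at baseline, each treatment block and each follow-up time "will be tested between the two treatment groups using SAS PROC GLM at each visit", and adds a PROC MIXED model with unstructured covariance. Sections 3.7.2.1.1 (MADRS), 3.7.2.2.1 (BDI) and 3.7.3.1.1 (QIDS-C16) follow the same pattern.

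**Missing data.** The only firm rule is in 3.1.1: patients who drop out during treatment are failures and "the missing values will not be imputed". That sentence is limited to drop-outs and to the primary analysis. Multiple imputation is optional for unnamed secondary analyses. Nothing gives the value or the denominator for a patient who stopped sessions because of remission.

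**Secondary endpoints.** Section 3.7.2.6 takes these, tested at 0.01, from the preceding analyses at the end of acute treatment. It does not say which record that is for a patient who finished early.

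**The concern.** At session 25, and perhaps at session 30, a rating can be absent because the patient has already succeeded. If rTMS works, more are absent for that reason in the rTMS arm. GENMOD and GLM drop rows with a missing outcome, so the late-block comparison would be between the patients of each arm who have not yet remitted, not between the randomised groups.

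At stake is the consistency of the short-term efficacy tables. A table labelled ITT could show remission percentages far below the primary result in the same patients, and the per-visit score tests would understate the difference. The open meaning of 30/last also bears on which MADRS, BDI and BSS record feeds the secondary endpoint tests.

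**Working it through.** **Inputs from the SAP.** Section 2.6: "With a sample size of 180 per group, the proposed study will have a power of 81" per cent, for "6% sham and 16% rTMS". Section 3.1.2: two-sided tests at 0.05.

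**Assumptions, not in the SAP.** Share of remissions reached by sessions 20 and 25: 25%/60%, 50%/75% or 75%/90%. For scores: HRSD SD 8.5, correlation between adjacent visits 0.6 to 0.9.

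**1. The plan's own figure.** Power = Φ[(d − 1.96·SE0)/SE1], with d = 0.10, SE0 = √(2·0.11·0.89/180) = 0.0330 and SE1 = √((0.06·0.94 + 0.16·0.84)/180) = 0.0326. This gives 86.1%. Subtracting the continuity correction 1/180 from d gives 82.0%, close to the stated 81%. The planning rates are usable as they stand.

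**2. Remission by block.** Let r20, r25 and r30 be the proportions first remitting at each session. The observed-case rate at session 25 is r25/(1 − r20), and at session 30 it is r30/(1 − r20 − r25). With the 50/25/25 split, rTMS has 8, 4 and 4 per 100 and sham has 3, 1.5 and 1.5.

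| | Observed only | Cumulative, all randomised |
|---|---|---|
| Session 25 | 4/92 = 4.3% v 1.5/97 = 1.5%; difference 2.8 points | 12.0% v 4.5%; difference 7.5 points |
| Session 30, block 6 read literally | 4/88 = 4.5% v 1.5/95.5 = 1.6%; difference 3.0 points | 16% v 6%; difference 10 points |

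Over the three timings the observed-only difference is 1.8 to 3.7 points at session 25 and 1.2 to 4.6 points at session 30.

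**3. Power (no continuity correction).** At session 25 with the 50/25/25 split, observed-only power is about 34%. For cumulative 12.0% v 4.5% with 180 per arm, SE0 = 0.0290 and SE1 = 0.0287, so (0.075 − 1.96·0.0290)/0.0287 = 0.63 and power is about 74%. At session 30, read literally, power is 18-51% over the three timings, against 86.1% for 16% v 6%.

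**4. Odds ratio.** At session 25 the observed odds are r25/(1 − r20 − r25) and the cumulative odds are (r20 + r25)/(1 − r20 − r25). The denominators are the same. The observed odds ratio therefore equals the cumulative one multiplied by the ratio, between arms, of r25/(r20 + r25).
- Same timing in both arms: that ratio is 1. Session 25 gives (4/88)/(1.5/95.5) = 2.89 and (12/88)/(4.5/95.5) = 2.89. Session 30 gives 2.98 both ways.
- Different timing: the odds ratio moves in either direction. With rTMS at 75%/90% and sham at 25%/60%, observed is (2.4/85.6)/(2.1/96.4) = 1.29 and cumulative is (14.4/85.6)/(3.6/96.4) = 4.50. With the timings swapped, observed is (5.6/90.4)/(0.9/94.6) = 6.51 and cumulative is (9.6/90.4)/(5.4/94.6) = 1.86.

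**5. HRSD scores.** Simulated multivariate normal scores at sessions 20, 25 and 30, with means giving 6% and 16% at or below 10 at session 30 and exit once a score is 10 or less:

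| Correlation | Session 25: true, observed only | Session 30: true, observed only |
|---|---|---|
| 0.6 | 4.24, 3.77 (−11%) | 4.73, 4.02 (−15%) |
| 0.8 | 4.24, 3.63 (−15%) | 4.77, 3.85 (−19%) |
| 0.9 | 4.26, 3.54 (−17%) | 4.75, 3.73 (−21%) |

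A likelihood estimate using all visits recovers 4.74-4.77 at session 30. In this simulation 8-11% of sham and 19-26% of rTMS patients have remitted by their last acute rating, more than the planning rates, so the losses are indicative rather than exact.

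**The case against.** **The SAP nowhere says that only observed patients are used.** That stands: it is inferred from the defaults of GENMOD and GLM. The rule against imputation does not supply it, because early remitters are not drop-outs and these are not the primary analysis. The omission remains, since no other rule covers these patients.

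**The footnote says that sessions may not be required, not that ratings stop, and 30/last naturally reads as the last acute rating.** This largely stands for session 30, which would then be repaired. It does not repair session 25: a patient who moves on to taper has no scheduled HRSD, MADRS, BDI or QIDS rating to fill that cell. BSS and BHS are less exposed, being rated in taper.

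**A reader might infer that the plan hides the treatment effect or biases it toward no effect.** The documents do not support that. The planned measure is the odds ratio, which is unchanged when timing is alike in both arms and can move either way when it is not. For scores, the planned unstructured PROC MIXED model uses the ratings that led to exit and is close to unbiased. Its compound-symmetry fallback and the default GLIMMIX pseudo-likelihood are less safe.

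**A reader might also infer that the primary result is at risk, or that a baseline odds ratio is planned.** Section 3.7.1.1 takes remission at the end of acute treatment, whenever that falls, so the primary result is not affected. Section 3.7.1.2.3 asks only for a baseline summary and does not specify a baseline test.

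**Conclusion.** The point holds for supportive analyses and should be fixed before analysis. Run as written with procedure defaults, early remitters leave the session-25 comparisons of remission, HRSD, MADRS, BDI and QIDS, and the session-30 ones too if 30/last is read literally. Under the 50/25/25 timing the session-25 risk difference is 2.8 points instead of 7.5, and power is about 34% instead of 74%. The odds ratio is preserved only if the timing of remission is alike in the two arms. Per-visit HRSD differences lose roughly 11-21%. All these sizes rest on assumed timing, SD and correlations, because the SAP gives none. The existence of the gap does not rest on those assumptions.

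**What to change.** - **Section 3.7.1.2.3:** report and test cumulative remission by block, with all randomised patients in the denominator. A patient who ended acute treatment in remission counts as remitted at later acute blocks; a drop-out counts as not remitted, as in the primary analysis. Show baseline remission as a descriptive count only.
- **Appendix 5.2 and Section 3.7.2.6:** state that 30/last is the last acute assessment for every patient, and that this is the end-of-acute record used for the secondary endpoints.
- **Sections 3.7.1.2.5, 3.7.2.1.1, 3.7.2.2.1 and 3.7.3.1.1:** at sessions 25 and 30, replace the per-visit GLM with visit contrasts from the unstructured mixed model. Keep the treatment-by-visit term for those contrasts. The present rule removes it when it is not significant, which would leave no visit-specific estimate.

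The cost is SAP wording and one derived status variable. No new data are needed, and the primary analysis does not change.
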